Measurements	Total intraoperative and postoperative opioid administration during hospitalization will be recorded from the patient's electronic medical record (EMR). Pain intensity will be assessed using the Numeric Rating Scale (NRS) and colored-visual analogue scale. Pain relief will be assessed using five point scale (0-no relief, 4-complete pain relief). Postoperative sedation will be recorded using Modified Observer's Assessment of Alertness/Sedation (MOAA/S). Assessment of opioid side effects will be performed using Opioid-Related Symptom Distress Scale (ORSDS). Daily opioid consumption and daily pain self-assessments using a colored-visual analogue scale will be recorded in a home diary for approx 30 days following surgery (from hospital discharge until postop clinic visit). Additional ORSDS assessments will be recorded at various timepoints (approx 7, 14 and 30 days postop) in the home diary. Subjects may have their CYP2B6 genotype determined.

Statistical Methodology	Demographic data including race, sex, and age will be analyzed using chi-square and t- test or ANOVA, as appropriate. Baseline characteristics of the cohort will be described. Total daily opioid consumption and pain scores using NRS, will be compared between the groups. Outcome measures will be expressed as the mean and standard deviation. Group outcomes will be compared across the two groups, using t-test and/or analysis of variance, ANOVA and MANCOVA to account for potential cofounders.
Outcomes	
Primary: Intraoperative and postoperative opioid utilization
 
Secondary:
 
 1) Opioid consumption and pain relief within first 30 postoperative days 2) Pain scores and pain self-assessments 3) Influence of CYP2B6*6 genotype on methadone clinical effectiveness for pain relief and opioid consumption

1. Specific Aims

- 1.1. To study the effects of a single dose of methadone on postoperative pain and opioid consumption in patients undergoing moderately painful, ambulatory surgical procedures.
- 1.2. Determine opioid consumption and pain relief within first 30 postoperative days
- 1.3. Determine cytochrome P4502B6 (CYP2B6) genotype in patients receiving methadone, and any relationship to postop pain relief and opioid consumption

2. Background

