Enrolled subjects will be asked to complete a questionnaire about their current pain and what they anticipate following surgery. Patients will receive standard physiologic monitoring for anesthesia and postoperative care. Subjects within each cohort (n≥60 evaluable, depending on the number of dose levels in each cohort) are randomized 1:2 to receive either control (typical intraop opioid, such as fentanyl or morphine) or methadone HCl (0.1 – 0.3 mg/kg ideal body weight, IBW). It is anticipated that the first ten patients will receive 0.1 mg/kg IV methadone. If patients still have significant post-op opioid requirements, subsequent groups may receive 0.2 mg/kg and then 0.3 mg/kg ideal body weight.

Anesthesia and surgical care will not be altered for the purposes of this investigation, except that subjects in methadone group will receive methadone as their intraoperative opioid, rather than leaving the choice of intraoperative opioid to the anesthesiologist. The control group patients will receive intraoperative analgesia with opioids other than methadone left at the discretion of their anesthesiologist (typically fentanyl or morphine).

Administration of Study Medication

Methadone is administered as an IV bolus at induction of anesthesia. Methadone hydrochloride is available commercially for injection (10 mg/ml). Subjects randomized to the control group will receive typical (non-methadone) opioids. Both groups will receive standard of care postoperative analgesia as determined by the treating physician. Postoperative care is not altered for purposes of this study.

Assessments

Pain assessments at rest (when patient awake) will be conducted in the postoperative period by a trained member of the research team. These will occur after handoff in the Postop Anesthesia Care Unit (PACU) and approx every 15 minutes during first PACU hour, then approx every hour for the next 4 hours and at bedtime. The pain assessments will also be performed at approx 24 hrs or prior to discharge from the hospital, whichever occurs first. Pain intensity will be assessed using the 0-10 Numeric Rating Scale and a colored-visual analogue scale. Pain relief will be assessed using five point scale (0-no relief, 4-complete

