pain relief). Observed sedation (Modified Observer's Assessment of Alertness/Sedation, MOAA/S) and subject's self-assessment of sedation are recorded at the same intervals as pain assessments. Assessment of opioid side effects is performed at approximately 24 hrs or prior to discharge from the hospital using Opioid-Related Symptom Distress Scale (ORSDS). The total amount of other drugs administered during hospitalization for prophylaxis or treatment of opioid side effects will be recorded from the EMR. Daily home opioid usage and pain self-assessments will be recorded in a home diary. The ORSDS assessments will also be completed at various timepoints (approximately 7, 14 and 30 days postop).

Any adverse events are described, recorded and reported according to GCP and IRB regulations.

7. Data Collection and Monitoring.

Opioid Consumption During Hospitalization

The EMR will be used to calculate the amount of morphine or morphine equivalents administered during surgery and until discharge, as well as other drug administration for treatment and/or prophylaxis of possible opioid side effects.

Follow-up Assessments

A home diary will be used to assess daily drug dosing history upon discharge from the hospital until the patient's postop clinic visit at approximately 30 days. Subjects will also record daily pain self-assessments using a colored-visual analogue scale (at rest, with activity and with coughing). The ORSDS will be completed and recorded on approximately the 7th, 14th and 30th day. We will also ask subjects about remaining number of pain medications and their disposal at the 30 day time point.

CYP Genotyping

Approximately 5 ml of blood will be collected from an IV line for CYP2B6 genotyping. Genotyping will be performed at the WUSTL Genome Technology Access Center (GTAC).

Other Measurements

Required baseline measurements that will be obtained from the EMR are age, vital signs, weight, height, and peripheral oxygen saturation by pulse oximetry and are all collected as standard of care.

8. Data and Safety Monitoring Plan.

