In general, the Department of Anesthesiology has developed a specific set of Standard Operating Procedures (SOPs) for clinical research. All individuals working on study are required to read and be totally familiar with and compliant with the SOPs. The SOPs are in part developed from and are compliant with the Institutional guidelines, including those for a) Interactions with the Washington University Human Subjects Review Committee, b) Informed Consent Development and Implementation, c) Subject Recruitment and Screening, d) Subject Management While on Study, e) Adverse Event Reporting. The specific plan for submitting Adverse Event Reports to the IRB is detailed in the SOP for Adverse Event Reporting.

The specific monitoring plan for this investigation is commensurate with the risks, size and complexity of the investigations planned. The potential risks are attributable to the use of methadone. Based on the small size and relatively low risks nature of the protocol, only the PI and CoI are involved in monitoring plan, rather than a full DSMB. These individuals will review the annual summary of adverse events. In addition, they will review all reports of a Serious Adverse Event, or an Unexpected Adverse Event.

9. Statistical Methods

Primary Assessment

Overall opioid (morphine equivalents) consumption for each patient during hospital stay
Absolute pain and sedation scores

CONFIDENTIAL: This document is the intellectual property of [name]. Acceptance of this document constitutes the agreement by the recipient that no unpublished information contained herein will be published or disclosed without prior written approval.

Secondary Assessments

Opioids (morphine equivalence) consumption within approx. first 30 postoperative days
 Postoperative pain self assessments
 CYP2B6*6 Genotype

Analysis

Sample Size: Our initial plan is to enroll ≥ 60 evaluable subjects in each of two cohorts for this pilot study. More specifically, this pilot plans 20 evaluable subjects in each methadone group within each cohort, with requisite proportional controls. Total number in each of the two cohorts will reflect the number of dose groups in each cohort (per escalation). Anticipated total evaluable is <200 .

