Statistical Analysis: Each cohort is analyzed separately. Baseline characteristics of each cohort and groups within each cohort will be described. Demographic data including race, sex, and age at study entry will be analyzed using chi-square and t-test or ANOVA, as appropriate. Total daily opioid consumption and pain scores using NRS will be compared between the groups. Outcome measures will be expressed by the mean and standard deviation. Group outcomes will be compared across the two groups, using t-test and/or analysis of variance, ANOVA and MANCOVA to account for potential cofounders.

10. Risk Assessment

Methadone

The most common side effect of opioids such as methadone is mild sedation. Since patients will be anesthetized during this period, clinical methadone effects are expected to be no different from those of anesthesia and any other opioid administered during anesthesia. The most common adverse effect of methadone is nausea and/or vomiting. Patients will have only clear liquids 6 hours before anesthesia, per standard of care. If nausea and/or vomiting occur, they will be treated using the standard of care for all post-anesthesia nausea and vomiting. Respiratory depression is a potential concern with all opioids, but has not been problematic at the doses of methadone that have been used in similar previous studies. Mild respiratory depression is defined as respiratory rate <8 /min in adults. Severe depression will be defined as the administration of naloxone to a patient with respiratory rate < 6 /min. If treatment is required, naloxone will be used. Patients in the hospital are routinely periodically monitored by blood pressure and/or pulse oximetry, and receive supplemental oxygen if dictated, according to good clinical practice.

Special Precautions

Standard of care for all surgical patients includes an IV, pulse oximetry, ECG, blood pressure monitoring.

Genotyping

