The dose of methadone given will be a standard analgesic dose, and it might provide longer pain relief than other opioids. The risk of respiratory depression is no more than that expected from standard morphine therapy as the patients will only receive one dose of methadone and it will be at doses less than treatment doses.

11. Human Subjects Research

Protection of Human Subjects

The study will be conducted under appropriate Washington University Institutional Review Board protocols and consent forms approvals. The study will be conducted under the supervision of the PI and Co-Investigator, who is a Board-Certified anesthesiologist with many years of experience in the conduct of human volunteer studies.

Sources of Materials

Information including demographic data, outpatient medications, chronic medical conditions, surgical procedure, length of stay, opioid and other drug administration and physiological monitoring will be obtained from the patient's electronic medical record.

Recruitment and Informed Consent

Patients will be screened based on operating room schedules, and approached prior to surgery at the Barnes-Jewish Hospital Center for Preoperative Planning and Assessment. All study related procedures, risks and benefits will be described to eligible patients, and time will be provided for addressing all questions and concerns.

Potential Benefits of the Proposed Research to the Subjects and Others

1) Prolonged analgesia from methadone is expected to decrease the need for additional opioids in the immediate postoperative period, 2) opioid quantities routinely prescribed upon discharge may be reduced with methadone us, 3) lower overall dose of opioids administered can decrease possible side effects of opioids, and 4) improved immediate postoperative pain relief may decrease the occurrence of chronic postoperative pain

Inclusion of Women

Studies and their advertisements actively encourage the participation of women in the research. Women of childbearing potential are not excluded from our research protocols. Pregnancy testing is performed as standard of care to protect female research subjects, and subjects are instructed when appropriate to use adequate contraceptive measures and avoid breastfeeding.

Inclusion of Minorities

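### The plan offers unadjusted and adjusted comparisons of the same outcome without saying which is the result, and does not prespecify use of the preoperative pain questionnaire

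*Combined protocol and SAP*

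**What the plan says.** The comparison is described in one sentence in Section 9 (Statistical Analysis), repeated in the synopsis under Statistical Methodology: outcomes in the two groups are compared "using t-test and/or analysis of variance, ANOVA and MANCOVA to account for potential cofounders". Neither place names a primary model, a covariate or a selection rule. The two cohorts are analysed separately. The first-listed primary assessment is "Overall opioid (morphine equivalents) consumption for each patient during hospital stay"; pain and sedation scores stand under the same label.

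Baseline information is collected in several places:
- Section 6 (Preoperative and Intraoperative Period): "Enrolled subjects will be asked to complete a questionnaire about their current pain and what they anticipate following surgery".
- Section 7 (Other Measurements): "Required baseline measurements that will be obtained from the EMR are age, vital signs, weight, height, and peripheral oxygen saturation by pulse oximetry".
- Section 11 (Sources of Materials): the record also supplies "surgical procedure, length of stay, opioid and other drug administration and physiological monitoring".

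None of these is given a role in the treatment comparison. Race, sex and age appear only in a between-group check: "Demographic data including race, sex, and age at study entry will be analyzed using chi-square and t-test or ANOVA, as appropriate".

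**The concern.** With two groups, a t-test and a one-way ANOVA are the same test, so the list is shorter than it looks. Three things remain open: whether to adjust, for which covariates, and whether outcomes are tested one at a time or jointly. Each choice gives a different p-value for the same opioid outcome, and nothing says which one is the trial's result.

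The plan justifies adjustment by confounding. In a randomised comparison the better reasons are precision and chance imbalance, and both call for covariates chosen in advance because they are expected to predict the outcome. Pain before surgery and pain expected after it are natural candidates and are already to be asked for. Precision matters because each cohort is analysed alone and may hold only about 60 subjects.

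MANCOVA's omnibus test is joint across outcomes, so it does not answer whether opioid use differed. The plan does not say which outcomes would enter it.

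**Working it through.** **The plan's own numbers.** Section 9 plans 20 evaluable subjects per methadone dose group in each cohort, with controls in proportion; within each cohort subjects "are randomized 1:2 to receive either control" or methadone. Two dose levels give 40 + 20 = 60 per cohort, matching the stated minimum. Three give 60 + 30 = 90 per cohort and 180 in all, within the stated ceiling of under 200. No alpha, power, effect size, SD or correlation is stated, so there is no power figure to reproduce.

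**Assumptions.** One cohort with 40 methadone (dose levels pooled) against 20 control, a true difference of 0.7 SD, and a two-sided 5% test. The multiple correlation r between the covariates and opioid use is unknown and is varied from 0 to 0.5.

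**Unadjusted power.** The standard error in SD units is sqrt(1/20 + 1/40) = 0.274, so the noncentrality is 0.7/0.274 = 2.56. With 58 degrees of freedom, power is 71%.

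**Adjusted power.** The simple factor 1 − r² ignores the cost of estimating covariate effects. With N subjects and k random covariates, the variance of the treatment effect is multiplied by (1 − r²)(N − 3)/(N − k − 3). At N = 60 the second factor is 57/55 = 1.036 for k = 2 and 57/52 = 1.096 for k = 5. Dividing 2.56 by the square root of the variance multiplier, with 58 − k degrees of freedom, gives the formula columns. The other columns are simulated power for the same settings.

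| r | variance, k = 2 | formula | simulated | variance, k = 5 | formula | simulated |
|---|---|---|---|---|---|---|
| 0 | 1.036 | 69% | 70% | 1.096 | 67% | 67% |
| 0.2 | 0.995 | 71% | 71% | 1.052 | 69% | 68% |
| 0.3 | 0.943 | 74% | 74% | 0.998 | 71% | 72% |
| 0.4 | 0.871 | 77% | 77% | 0.921 | 74% | 74% |
| 0.5 | 0.777 | 81% | 80% | 0.822 | 79% | 80% |

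Two pain scores gain nothing at r = 0.2, about 3 points at 0.3, 6 at 0.4 and 9 to 10 at 0.5. They cost 1 to 2 points if they predict nothing. Five covariate terms, roughly the two scores plus a four-category procedure factor, give no real gain at r = 0.3 and lose power below it.

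**Type I error.** Simulated under no treatment effect, 40 against 20, nominal 5%:
- One model fixed in advance: about 5%.
- Smaller p of the unadjusted test and one single-covariate model: about 6.5% (6.4% to 6.7% for correlations of 0.2 to 0.4).
- Smallest p among the unadjusted, each single-covariate and the full model, with 4 to 6 candidate covariates and total R² of 0.2: 9% to 10%.

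**The case against.** The strongest reply is that this is a self-described pilot with no stated alpha or power, so confirmatory error control matters less, and that the benefit of adjustment rests on a correlation the documents do not supply. The questionnaire is about pain, while the lead outcome is opioid use that includes the intraoperative period. Both points stand and limit the size of the concern. They do not remove it: the objective is efficacy, between-group tests are planned, and the reader still cannot tell which test is the result.

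A reader might infer more than the documents support:
- *That the questionnaire and procedure go unused.* The reference to potential confounders is open-ended and could include them. What can be said is that their use is not prespecified.
- *That every subject will have two pain scores.* Subjects are asked to complete a questionnaire. Its scale is not given, and it is not among the required baseline measurements in Section 7.
- *That MANCOVA yields no opioid estimate.* The multivariate model gives an adjusted coefficient for each outcome, equal to the ANCOVA on the same complete cases. Only the omnibus test is joint. How many subjects it would drop cannot be judged, because its outcomes are not listed.
- *That false positives will run at 9% to 10%.* That requires reporting the smallest p-value. Nothing says this will be done, and choosing covariates from significant baseline tests gave only 4% to 5% in simulation.
- *That adjustment is free.* With many terms and weak predictors it loses power.

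**Conclusion.** The point holds in a limited form. The plan permits several analyses of the same outcome without choosing one, and assigns no role to preoperative pain data it intends to collect. The precision at stake is modest: between a small loss and about 10 points of power, depending on a correlation between 0 and 0.5 that is assumed. The figures also assume pooled dose levels, 40 against 20 subjects, a 0.7 SD difference and a two-sided 5% test. The error at stake is at most a rise from 5% to about 6.5%, or to 9% to 10% with 4 to 6 candidate covariates, if the most favourable model were reported. The firmer reason to act is that the primary result would be defined before the data are seen.

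**What to change.** In Section 9 and the synopsis, replace the list of methods with one primary analysis per cohort: an ANCOVA of in-hospital morphine equivalents on treatment, preoperative current-pain score and anticipated-pain score, used whatever the baseline tests show. In addition:
- State how the questionnaire is scored, and keep subjects with a missing questionnaire through simple baseline imputation.
- Report the unadjusted difference as supportive.
- Replace MANCOVA with the same ANCOVA run separately for each other outcome, including the pain scores.
- Add procedure group only if it can be held to one or two terms set beforehand.
- Say how skewed opioid totals will be handled.

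The cost is a paragraph of text and two degrees of freedom per cohort, with no new data or patient burden. The downside is a loss of 1 to 2 points of power if the pain scores prove unrelated to opioid use.

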Study Design	Single-center, randomized, single blinded, positive-controlled dose escalation pilot study. Patients receive standard monitoring for anesthesia and postoperative care. Surgical and anesthesia care (except for intraoperative opioid use) are not altered for study purposes. In each cohort, subjects are randomized 1:2 to either control (standard intraop opioid at anesthesiologists' discretion, not methadone) or methadone HCl (0.1 – 0.3 mg/kg ideal body weight, IBW). Subjects in Group I will receive methadone (IV bolus, at induction of anesthesia) as their primary intraoperative opioid. Dose of methadone may be increased up to 0.3 mg/kg IBW following preliminary analysis and review of initial subjects enrolled to Group I. Subjects in Group II (control) will receive intraoperative opioid administration at the discretion of the anesthesia providers (typically fentanyl or morphine). Postoperative pain management for both groups will be per standard of care.
Inclusion and Exclusion Criteria	
Inclusion Criteria
 
 1. Age 18-65 years 2. Undergoing general anesthesia and moderately painful, ambulatory surgical procedures, with anticipated postop stay of < 24 hours 3. Signed, written, informed consent 
Exclusion Criteria
 
 1. History of liver or kidney disease. 2. Females who are pregnant or nursing. 3. Opioid tolerant patients (e.g. preoperative methadone therapy or use of fentanyl transdermal patches) 4. History of allergy to methadone

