We propose to evaluate intraoperative and postoperative opioid consumption, pain intensity and pain relief in patients undergoing moderately painful, ambulatory surgical procedures (anticipated length of stay <24 hrs) in 2 cohorts, and 2 groups in each cohort. Cohort 1 is ambulatory patients with <24 hr overnight stay, cohort 2 is same-day surgery outpatients). In each cohort, Group I will receive a single dose of methadone during surgery and Group II will receive a non-methadone intraoperative opioid (typically fentanyl or morphine). Secondly, we will study opioid consumption and pain self-assessments within approximately the first 30 postoperative days, or until the initial postop clinic visit.

3. Drug Information

Methadone hydrochloride is a synthetic μ -agonist with multiple actions qualitatively similar to those of morphine. Onset of effect is about 2-10 min for parenteral dosing. Methadone is primarily metabolized by N-demethylation to an inactive metabolite, 2-ethylidene-1,5-dimethyl-3,3-diphenylpyrrolidene (EDDP). In vivo, CYP2B6 is a major determinant of metabolism to inactive metabolites which are excreted mainly in the urine. The terminal half-life ($T_{1/2}$) in healthy adults averages 24-36 hrs (11, 12).

CONFIDENTIAL: This document is the intellectual property of [name]. Acceptance of this document constitutes the agreement by the recipient that no unpublished information contained herein will be published or disclosed without prior written approval.

The most common side effect of methadone, like other opioids, is sedation, nausea and vomiting. Respiratory depression is the chief hazard associated with methadone, like all opioids.

4. Eligibility

Inclusion Criteria

- Age 18-65 years
- Undergoing general anesthesia and moderately painful, ambulatory surgical procedures with anticipated postop hospital stay of < 24 hours
- Signed, written, informed consent

Exclusion Criteria

- History of or known liver or kidney disease.
- Females who are pregnant or nursing.
- Opioid tolerant patients (e.g. preoperative methadone therapy or use of fentanyl transdermal patches)
- History of allergy to methadone

5. Enrollment

Subjects will be approached prior to surgery in the Center for Preoperative Assessment and Planning or preoperative holding area. Patients will be consented for participation and enrolled in the study by trained study personnel.

6. Methods

Preoperative and Intraoperative Period

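### A respiratory rate below 6/min is graded severe only if naloxone was given, and no opioid side-effect form is scheduled between about 24 hours or discharge and day 7

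*Combined protocol and SAP*

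**What the plan says.** **Respiratory depression.** Section 3 (Drug Information) states: "Respiratory depression is the chief hazard associated with methadone, like all opioids". Section 10 (Risk Assessment, Methadone) gives two grades and no others: "Mild respiratory depression is defined as respiratory rate <8 /min in adults", and "Severe depression will be defined as the administration of naloxone to a patient with respiratory rate < 6 /min". On treatment it says: "If treatment is required, naloxone will be used". No rate or saturation value is given at which naloxone must be used.

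**Who knows the group.** The Synopsis describes a "Single-center, randomized, single blinded, positive-controlled dose escalation pilot study". Under Section 6, control patients receive "opioids other than methadone left at the discretion of their anesthesiologist", so the anesthesiologist knows the assignment. Whether recovery staff are blinded is not stated.

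**Side-effect forms.** Section 6 (Assessments) schedules the ORSDS at about 24 hours or before discharge. Sections 6 and 7 and the Synopsis then place it at about days 7, 14 and 30, and the Synopsis puts these later forms in the home diary. In the days between, the diary is described as collecting daily opioid use and pain ratings. Section 6 also says that any adverse event is recorded and reported.

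**The concern.** The severe grade joins a physiological finding (rate below 6/min) to a clinician's action (giving naloxone). A patient who breathes at 5/min and is stimulated, watched or given oxygen instead of naloxone falls into the same grade as one at 7/min. A safety table built on these definitions would show some of the slowest breathing as mild, and would also place reversal at 6 or 7/min under mild. That is an unhelpful way to describe what the protocol calls the chief hazard.

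The second point is one of timing. Section 2 gives fewer opioid side effects as part of the rationale, and the Abstract says that nothing is known about methadone in ambulatory patients. The first days at home are therefore of particular interest, above all in the same-day cohort, yet the structured side-effect form skips them.

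**Working it through.** **1. Grading.** Inputs: the two definitions in Section 10, applied literally. Mild has no lower bound, and severe needs both conditions. The last column applies the rule proposed under the fix.

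| Respiratory rate | Naloxone for respiratory depression | Grade as written | Grade under the proposed rule |
|---|---|---|---|
| 5/min | no | mild | severe |
| 5/min | yes | severe | severe |
| 6 or 7/min | no | mild | mild |
| 6 or 7/min | yes | mild | severe |
| 8/min or more | no | none | none |
| 8/min or more | yes | none | severe |

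The first and fourth rows are the problem.

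For scale only: Section 9 says "this pilot plans 20 evaluable subjects in each methadone group within each cohort". One regraded patient therefore moves the severe proportion in a dose group by 1/20 = 5 percentage points. That holds for any yes/no event in 20 patients. It does not estimate how often regrading would occur. The documents give neither the frequency of rates below 6/min nor the share treated with naloxone, so nothing further can be computed.

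**2. Length of the ORSDS gap.** Day 7 is 7 × 24 = 168 h. Same-day discharge at 4 to 8 h is an assumption, since the documents give no discharge time.

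- After a 24 h form: 168 − 24 = 144 h = 6.0 days.
- After discharge at 8 h: 168 − 8 = 160 h = 6.7 days.
- After discharge at 4 h: 168 − 4 = 164 h = 6.8 days.

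**3. Drug present during the gap.** Input: the half-life of 24 to 36 h in Sections 2 and 3. Fraction left after time t = 0.5^(t / half-life). This is a single-exponential simplification that ignores early distribution.

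| Interval | Half-life 24 h | Half-life 36 h |
|---|---|---|
| Left at 24 h, share of dose | 50% | 63% |
| Left at 168 h, share of dose | 0.8% | 3.9% |
| Of the amount present at 24 h, left at 168 h | 0.5^(144/24) = 1.6% | 0.5^(144/36) = 6.25% |
| Of the amount present at 24 h, left at 72 h | 0.5^(48/24) = 25% | 0.5^(48/36) = 39.7% |

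So 94% to 98% of the methadone present at 24 h is gone by the day-7 form, and 60% to 75% of it by day 3. For a same-day patient whose form is completed at 6 h (assumed), 84% to 89% of the dose is left at the form and 0.8% to 3.9% at day 7. About 83% to 85% of the dose is thus eliminated between the two forms (84.1 − 0.8 = 83.3; 89.1 − 3.9 = 85.2). These figures describe amount of drug, not frequency of side effects.

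**The case against.** The strongest reply on grading is that nothing depends on it. The definitions sit in the risk section, neither the Synopsis outcomes nor Section 9 lists respiratory depression, and no between-group comparison of grades is planned. This is correct and keeps the severity low. It is also fair that the data may be recoverable: Section 11 (Sources of Materials) says "length of stay, opioid and other drug administration and physiological monitoring will be obtained from the" electronic record, so events could be regraded at reporting if rate and naloxone are charted. That makes the change cheap; it does not make the written rule right.

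A reader might infer from the single blinding that severe counts would be biased between the arms. The documents do not support that. Different naloxone thresholds by group are possible, but nothing shows that they would occur or in which direction, and no event or treatment rate is given from which to size an effect.

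Simply grading on the lowest charted rate would also be wrong. Methadone is given at induction, so rates under anesthesia could count as events, and a patient reversed at 7/min would stay mild. The rule needs a time window and must keep naloxone as a sufficient condition.

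On the ORSDS, days 7, 14 and 30 are a legitimate choice for a measure that is not a listed outcome. A reader might infer that safety goes unobserved between discharge and day 7. That is not so: adverse events are recorded throughout, Section 8 refers to a reporting procedure that is not among the documents, and the ORSDS recall period is not given. If the day-7 form asks about the preceding week, it covers most of the gap by recall.

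**Conclusion.** Both points hold, at low severity. As written, the severe grade misses any rate below 6/min that was not treated with naloxone, and any reversal at 6/min or above. The effect is confined to safety reporting that uses the Section 10 definitions; the primary outcome, sample size and planned analyses are untouched. The size of any misgrading cannot be stated from the documents.

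The ORSDS gap of about 6 to 7 days is confirmed in every place where the schedule appears. The 6.0 days rests on a form at 24 h, and the 6.7 to 6.8 days on an assumed discharge at 4 to 8 h. It spans the elimination of nearly all the methadone still present at 24 h. Earlier forms would improve capture of early side effects at home. They would not fill a complete safety gap, and a symptom questionnaire is not a monitor for respiratory depression.

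**What to change.** **Section 10.** For the period from emergence from anesthesia until discharge, define severe respiratory depression as a respiratory rate below 6/min or naloxone given for respiratory depression. Define mild as a rate of 6 to below 8/min without naloxone. Report naloxone use separately by group, because under this rule it still decides the grade at rates of 6/min and above. The cost is wording only, provided that respiratory rate is charted. The definitions imply that it is, but Section 10 names only blood pressure and/or pulse oximetry as routine periodic monitoring, so this should be confirmed.

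**Section 7.** Add the ORSDS to the home diary on days 1 to 3 in both cohorts. In overnight patients the 24 h form can serve as day 1. The cost is two extra short forms for overnight patients and three for same-day patients, in a diary that they already complete daily. Neither change alters the sample size.
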